14.2. Evaluation of Adverse Events

Adverse events include:

- Suspected adverse drug reactions
- Reactions from study drug overdose, abuse, withdrawal, sensitivity, or toxicity
- Significant changes or abnormalities when compared to baseline, in signs, symptoms, clinical laboratory results, or physiological testing. This includes any worsening of a pre-existing condition temporally associated with the use of study drug.
- Other untoward medical events, regardless of their relationship to the study drug, such as injury, events that require surgery, accidents, extensions of symptoms, or apparently unrelated illnesses

The following considerations apply when identifying an AE:

- Anticipated day-to-day fluctuations of pre-existing conditions, including the disease under study, that do not represent a clinically significant exacerbation or worsening need not be considered AEs.

- If a constellation of symptoms results in a confirmed diagnosis, the diagnosis (not the symptoms) should be recorded as the AE term.
- If a diagnosis cannot be established, the symptoms should be recorded as the AEs.
- If an ongoing symptom has been included in the medical history, an associated severity grade and frequency should also be documented so that a worsening in severity or frequency of a symptom can be readily identified as an AE.
- Progression of disease is not itself an AE unless the progression of disease is assessed by the investigator as related to the study treatments; however, the presenting sign or symptom of the disease progression should be documented as an AE (e.g., increase in pain). Death due to “progression of disease” within the SAE reporting period (from the signing of the ICF until 90 days after the last dose of any study treatments) should be reported as SAE.

Adverse events will be followed from the next study until resolution or to the end of the follow-up period. AEs that are drug-related should be followed until resolved or no resolution is expected.

14.3. Determination of Seriousness

14.3.1. Serious Adverse Event

An AE is considered an SAE if at least one of the following conditions applies:

- Death: An AE that results in death during the active study period or within 90 days following study drug administration. In addition, a reported death at any time post-study that is thought to be related to study drug administration.
- Life-threatening AE: An AE that places the subject, in the view of the investigator, at immediate risk of death from the event as it occurred (i.e., this does not include a reaction that, had it occurred in a more severe form, might have caused death).
- Permanent, persistent, or significant disability: A disability is defined as any substantial disruption of a person’s ability to conduct normal life functions.
- Inpatient hospitalization or prolongation of existing hospitalization: In general, hospitalization refers to admission of a subject into a hospital for at least a 24-hour stay. Hospitalizations for routine blood transfusions, hospitalization for an elective or diagnostic procedure, or surgery for a pre-existing condition that has not worsened, are not considered SAEs. Emergency room visits that do not result with admission are not considered as SAEs.
- A congenital anomaly/birth defect: A fixed, permanent impairment established at or before birth.
- Important medical event: Events that may not result in death, be life-threatening, or require hospitalization may be considered SAEs when, based upon appropriate medical judgment, they jeopardize the subject and require medical or surgical intervention to prevent a life-threatening situation, hospitalization or death.

14.3.2. Non-Serious Adverse Event

An AE that does not fulfill the criteria for a SAE is classified as a non-serious AE.

14.4. Determination of Severity

The severity of AEs will be assessed according to the NCI CTCAE, Version 5. If an AE is not specifically defined in the NCI CTCAE, v5.0, the investigator will determine the severity of an AE based on the following general definitions recommended (National Cancer Institute 2017):

- Mild (Grade 1): The AE is noticeable to the subject but does not interfere with routine activity. The AE does not require discontinuing administration or reducing the dose of the study drug.
- Moderate (Grade 2): The AE interferes with routine activity but responds to symptomatic therapy or rest. The AE may require reducing the dose, but not discontinuation of administration of the study drug.
- Severe (Grade 3): The AE significantly limits the subject's ability to perform routine activities despite symptomatic therapy. In addition, the AE leads to discontinuation of administration or reducing the dose of the study drug.
- Life-threatening (Grade 4): The AE requires discontinuing administration of the study drug. The subject is at immediate risk of death.
- Death (Grade 5): The subject dies as a direct result of the complication or condition.

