10.10. Dose Modifications and Dose Delays

Veledimex dose delays and dose reductions for individual subjects will be allowed in the event of an adverse event, according to the criteria shown in Table 2.

Table 2: Criteria for Dose Delay and Dose Reduction of veledimex

Adverse Reaction	Severity ²	Veledimex Dosage Modifications ¹
Immediately life-threatening/ Potentially-Fatal Severe Adverse Reactions		
Any non-hematologic AE ³	Grade 4 non-hematologic adverse event at least possibly related to study drug, that is considered by the treating physician to be immediately life-threatening, and results in emergent medical and/or surgical intervention	Discontinue
Other Severe Adverse Reactions		
Cytokine Release Syndrome	Grade 3 or higher (per the Ziopharm Working Definition of Cytokine Release Syndrome)	Withhold ⁴
Any non-hematologic AE ^{3, 5} (except brain edema)	Grade 3 or higher non-hematologic adverse event that is at least possibly related to study drug and persists at least 3 days	Withhold ⁴
Cerebral edema ⁵	Grade 3 or higher	Withhold ^{4, 6}
Thrombocytopenia	Grade 3 or higher thrombocytopenia (< 50,000/mm ³) at least possibly related to study drug	Withhold ⁴
Lymphopenia or other hematologic toxicity	Grade 4 or higher lymphopenia or other hematologic toxicity (except thrombocytopenia)	Withhold ⁴
Increased transaminitis ⁸	Grade 3 or higher increase in ALT or AST	Potentially Withhold ⁷

1. These recommendations are for general guidance only. Treating physicians should manage patients according to their clinical judgement, as informed by institutional guidelines, best practices and these guideline recommendations.
2. Toxicity as graded per National Cancer Institute Common Terminology Criteria for Adverse Events, Version 5.0.
3. Nausea and vomiting will not be considered in this category unless at least Grade 3 or 4 and refractory to antiemetics (i.e., defined as symptoms not mitigated by maximal medical support as directed by the Investigator (per institutional guidelines) in consultation with the Sponsor Clinical Medical Monitor).
4. Withhold the next and any successive doses of veledimex while the Grade 3 or 4 toxicity persists. Veledimex dosing may resume, after discussion with the Sponsor Clinical Medical Monitor, in subjects with rapid and substantial reversal of toxicity, either spontaneously or following appropriate medical treatment. The Sponsor Clinical Study Coordinator will be notified in advance of veledimex dosage modifications.

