Table 14.3.1.9	Treatment Emergent Adverse Events by System Organ Class, Preferred Term and Severity	Full Analysis Population	AEs	
Table 14.3.1.10	Treatment Emergent Adverse Events by System Organ Class, Preferred Term and Severity with CTCAE Toxicity Grade ≥ 3	Full Analysis Population	AESev	
Table 14.3.1.11	Serious Adverse Events by System Organ Class and Preferred Term	Full Analysis Population	AESev	
Table 14.3.1.12	Treatment Emergent Adverse Events by Preferred Term in Decreasing Frequency	Full Analysis Population	AEPT	
Table 14.3.1.13	Treatment-Related Treatment Emergent Adverse Events by Preferred Term in Decreasing Frequency	Full Analysis Population	AEPT	
Table 14.3.4.1	Listing of Abnormal Laboratory Values		Sig_lab	
Table 14.3.4.2	Listing of Clinically Significant Laboratory Values		Sig_lab	
Table 14.3.5.1	Ad-RTS-hIL-12 Injections	Full Analysis Population	Exp1	
Table 14.3.5.2	Veledimex Exposure	Full Analysis Population	Exp2	
Table 14.3.5.3	Cemipluma Exposure	Full Analysis Population	Exp3	
Table 14.3.6.1	Summary of Serum Chemistry Results	Full Analysis Population	Lab	
Table 14.3.6.2	Clinical Significance of Serum Chemistry Results	Full Analysis Population	Lab2	
Table 14.3.6.3	Summary of Hematology Results	Full Analysis Population	Lab	
Table 14.3.6.4	Clinical Significance of Hematology Results	Full Analysis Population	Lab2	
Table 14.3.6.5	Summary of Coagulation Results	Full Analysis Population	Lab	
Table 14.3.6.6	Clinical Significance of Coagulation Results	Full Analysis Population	Lab2	

Table 14.3.6.7	Summary of Urinalysis Results	Full Analysis Population	Lab	
Table 14.3.6.8	Clinical Significance of Urinalysis Results	Full Analysis Population	Lab2	
Table 14.3.7	Summary of KPS	Full Analysis Population	KPS	
Table 14.3.8	Summary of Vital Signs	Full Analysis Population	Vitals	
Table 14.3.9	Summary of Weight	Full Analysis Population	Weight	
Table 14.3.10	Targeted Neurological Exam	Full Analysis Population	Neuro	
Table 14.3.11	ECG Findings	Full Analysis Population	ECG1	
Table 14.3.12	Summary of ECG Results	Full Analysis Population	ECG2	
Table 14.3.13	Dose Limiting Toxicities	Per Protocol Population	DLT	
Figure 14.2.3	Kaplan Meier plot of Progression Free Survival by Veledimex Dose			
Figure 14.2.4	Kaplan Meier plot of Overall Survival by Veledimex Dose			

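### For adverse events that CTCAE v5.0 does not define, the fallback Grades 3 and 4 in Protocol Section 14.4 require a study-drug action, so some severe events fit no grade

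*Protocol*

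**What the plan says.** Protocol Section 14.4 begins with the standard scale: "The severity of AEs will be assessed according to the NCI CTCAE, Version 5". Its own definitions are a fallback: "If an AE is not specifically defined in the NCI CTCAE, v5.0, the investigator will determine the severity" from a list of five grades. In that list:

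- Grade 1 says that no stop or dose reduction is needed.
- Grade 2: "The AE interferes with routine activity but responds to symptomatic therapy or rest". A dose reduction may be needed, but not a stop.
- Grade 3 is a marked limit on daily activity that persists under symptomatic treatment, followed by "In addition, the AE leads to discontinuation of administration or reducing the dose of the study drug".
- Grade 4 is an immediate threat to life, with the statement "The AE requires discontinuing administration of the study drug".
- Grade 5 is death, with no drug clause.

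Protocol Section 14.6 collects AEs from consent to 90 days after the last dose of any study drug, and records action taken separately from severity. SAP Section 9.1.1 also runs the treatment-emergent (TEAE) window to 90 days after stopping. SAP Section 9.1.5 tabulates TEAEs by severity. It shows a missing severity as Severe in tables and leaves it missing in the listing. The SAP appendices plan Table 14.3.1.10, "Treatment Emergent Adverse Events by System Organ Class, Preferred Term and Severity with CTCAE Toxicity Grade ≥ 3", and Listing 16.2.7.6 for the same grades.

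**The concern.** Severity describes the event, and action taken describes the response to it. When the response is a condition of the grade, the same event can be graded differently according to whether a dose was still due or what the physician chose to do. The safety profile is a primary endpoint in the Protocol Synopsis, and Grade 3 or higher TEAEs have their own table and listing. A grade that follows dosing status rather than clinical impact makes those outputs harder to interpret.

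**Working it through.** The plan states no figure to reproduce. The check takes each kind of event and tests it against the definitions.

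**Inputs.**
- Grading scale and its scope: Protocol 14.4.
- Separate scale for cytokine release syndrome (CRS): Protocol 10.11 and Appendix 1.
- Collection windows: Protocol 14.6 and SAP 9.1.1.
- Cemiplimab spacing: a minimum of 21 days between doses, with delays of up to 14 days for toxicity (Protocol Table 1 footnotes).
- Denominator: 40 subjects in the Full Analysis Set (SAP 4.4 and 9.1.5).

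**Step 1: which scale applies.** An AE with a CTCAE v5.0 definition takes its grade from CTCAE, and Section 14.4 adds no drug-action condition. CRS is graded by Appendix 1. Only the remaining AEs use the fallback list.

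**Step 2: severe, non-responding AEs on the fallback list.**

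| Situation | Grade 2 (responds to therapy or rest) | Drug-action clause | Grade as written |
|---|---|---|---|
| Drug stopped or reduced | Not met | Met | 3 |
| Starts when no further dosing is planned | Not met | Cannot be met | None fits |
| Dose held, then resumed | Not met | Met only if a hold counts as discontinuation | 3 or none |
| Life-threatening, no further dosing planned | Not met | No drug left to discontinue | 4 only if the clause is read hypothetically |

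The second row is the clear gap. The third depends on a term that Section 14.4 does not define.

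**Step 3: when no drug action remains.** This is not automatically the whole 90 days after the last dose. Whether to give the next cemiplimab dose stays open for at least 21 days, and with a permitted delay for 21 + 14 = 35 days. An AE that ends treatment in that interval does lead to discontinuation and can satisfy Grade 3. If treatment ends only because the next dose is not given, 90 − 35 = 55 to 90 − 21 = 69 days remain with no dose decision left. If the decision to stop was made at the last dose, the figure is up to 90. These are days of calendar time, not counts of events.

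**Step 4: what the tables show.** If the site picks the nearest grade, Grade 2, the event is absent from Table 14.3.1.10. If the site leaves the grade blank, the severity table shows it as Severe. The SAP does not say whether that convention carries over to Table 14.3.1.10 or Listing 16.2.7.6. Two sites with the same event can therefore produce different entries.

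**Step 5: scale.** One affected subject moves the row for that preferred term by 1/40 = 2.5 percentage points, and two by 2/40 = 5.0. An overall Grade 3 or higher count moves only if that subject has no other such TEAE. The number affected is not in the documents; zero to two is an assumed range for illustration.

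**Step 6: after removing the drug clauses.** The grades still separate: noticeable without interference; interferes but responds; markedly limiting despite treatment; immediate threat to life. The event in the second row becomes Grade 3.

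**The case against.** Several stronger readings are tempting, and the documents do not support them.

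A reader might infer that no severe event that is only held, or that starts off drug, can reach Grade 3. That ignores the sentence limiting the fallback list to AEs outside CTCAE. For all other AEs, Grade 3 and Grade 4 remain available whatever is done with the drug.

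A reader might infer that Section 14.4 contradicts Table 2 in Section 10.10, or that grading is circular because Table 2 uses grade to choose the action. One Table 2 row covers a "Grade 3 or higher non-hematologic adverse event that is at least possibly related to study drug and persists at least 3 days", and its action is to withhold. But the table's footnotes take grades from CTCAE v5.0 and describe the recommendations as general guidance. For CTCAE-graded events there is neither conflict nor circle. For fallback events the difficulty depends on whether a hold is a discontinuation. Table 2 lists the two as separate actions, which suggests it is not. Table 3 adds the word permanently when it means a final stop, which suggests the bare term could be wider. This is an ambiguity, not a proven failure.

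A reader might turn the 90-day window into a large share of follow-up in which severe events cannot be graded. Step 3 shows that part of the window can still carry a dosing decision. A share of time also says nothing about how many AEs fall outside CTCAE.

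A reader might infer that affected events disappear. SAP 9.1.5 moves ungraded events up to Severe, and SAP 9.1.3 lists all AEs. Seriousness (Protocol 14.3.1) does not use the Section 14.4 grade. The only grade-based trigger in the stopping rules (Protocol 10.9) is Grade 4 hematologic toxicity, and the toxicity boundary in Section 16.2 counts subjects who meet those rules.

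These limits stand. They do not fill the gap for a severe, non-responding, non-CTCAE event with no dosing left: the written rule gives it no grade.

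**Conclusion.** The point holds for AEs not specifically defined in CTCAE v5.0, and only for those. Fallback Grade 3 requires discontinuation or dose reduction, and fallback Grade 4 requires discontinuation. A severe event that does not respond to treatment and starts when no further dosing is planned meets neither Grade 2 nor Grade 3. For an event managed only by a hold, the same conclusion rests on reading a hold as something other than discontinuation.

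The direction of any error is not fixed: grading down lowers the Grade 3 or higher count, while a blank is shown as Severe in the severity table. The size cannot be computed because the documents do not say how many AEs use the fallback scale; that it is small is a judgement. No safety decision is shown to change. This is a minor defect in measuring part of a primary endpoint, worth correcting because the correction is simple.

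**What to change.** In Protocol Section 14.4, delete the clauses about stopping or reducing study drug from fallback Grades 1 to 4, and grade on functional impact and risk to life only. Keep action taken as the separate eCRF item under Section 14.6, and align the eCRF guidance. No dosing, hold or stopping rule changes.

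SAP Section 4.4 already counts 40 treated subjects, so new wording alone will not regrade recorded events. SAP Section 4.4.1 treats database lock as still to come. Before lock, identify the AEs graded on the fallback scale and query their grades on clinical impact alone. Also state in SAP Section 9.1.5 whether the missing-severity convention applies to Table 14.3.1.10 and Listing 16.2.7.6.

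The cost is a wording change and a query round limited to fallback-graded AEs. The Grade 3 or higher count may be slightly higher.

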14.5. Determination of Causality

The investigator will use medical consideration to determine the potential relationship of the AE to the study drugs based on his/her clinical judgment. Assessment of causality will be based upon the following:

- Alternative possible causes of the AE, including the subject's underlying disease or comorbid conditions, other drugs, other host, and environmental factors
- The temporal sequence between the exposure to study drug and the AE
- Whether the clinical or laboratory manifestations of the AE are consistent with known actions or previously reported toxicity of the study drug or similar drugs
- Whether the AE resolved or improved with decreasing the dose or stopping the study drug (i.e., dechallenge); or recurred or worsened with re-exposure to the drug (i.e., rechallenge).

Relationship assessments that indicate "Not Related" to investigational product:

- None: The event is related to an etiology other than the investigational product (the alternative etiology must be documented in the study subject's medical record and/or SAE form).
- Unlikely or Remote: The event is unlikely to be related to the investigational product and likely to be related to factors other than investigational product.

Relationship assessments that indicate "Related" to investigational product:

- Possible: There is an association between the event and the administration of the investigational product and there is a plausible mechanism for the event to be related

to investigational product; but there may also be alternative etiology, such as characteristics of the subject's clinical status or underlying disease.

- Probable: There is an association between the event and the administration of investigational product, a plausible mechanism for the event to be related to the investigational product and the event could not be reasonably explained by known characteristics of the subject's clinical status or an alternative etiology is not apparent.
- Definite: There is an association between the event and the administration of investigational product, a plausible mechanism for the event to be related to the investigational product and causes other than the investigational product has been ruled out and/or the event re-appeared on re-exposure to the investigational product.

For AEs that occur prior to the administration of investigational product, an assessment of protocol relatedness must be made. AEs may occur due to procedures required during the screening process (e.g., blood collection, washout of an existing medication) prior to the initial administration of investigational product. For AEs that occur before administration of investigational product, only those that are assessed by the investigator as protocol-related should be reported to the sponsor. The following guidelines should be used by investigators to assess the relationship of an AE to a protocol-required procedure:

- Protocol-related: The event occurred due to a procedure or intervention that was described in the protocol for which there is no alternative etiology present in the subject's medical record.
- Not protocol-related: The event is related to an etiology other than the study procedure (the alternative etiology must be documented in the study subject's medical record).

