12.3.2.18. Unscheduled Visits Collections

In the event of subject termination or an unscheduled visit for a drug-related AE, an unscheduled visit kit should be obtained for cytokines and immunological markers for CSF evaluation, if applicable.

At all visits, concomitant medications, adverse events, and survival status will be documented. Concomitant medications will be monitored and recorded throughout the study. Medications

received in the period preceding consent (~28 days), in addition to those ongoing at screening, will be captured in the eCRF. Non-serious events from ICF signature until administration of first study drug that are not study related will be reported as medical history. Concomitant medications and AEs/SAEs must be recorded in the eCRF through 90 days after the last dose of any study drug. Ongoing drug-related AEs should be followed until resolution unless none is expected. New anti-cancer medications should be captured through completion of survival follow-up.

Refer to Synopsis [Table 1](#) for Schedule of Study Procedures.

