14.6. Documenting Adverse Events

All AEs, including SAEs, are to be accurately recorded on the Adverse Event page of the subject's eCRF from the time the subject signs the informed consent through 90 days after the subject's last dose of any study drug. Each event will be assessed for serious criteria, severity, and causality ([Section 14.5](#)). The date of onset, as well as the duration of the event will be recorded. In addition, treatments provided to the subject, actions taken with the study drugs, and the outcome of the AE will also be noted.

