14.7. Reporting Serious Adverse Events (SAE), and Adverse Events of Special interest (AESI)

14.7.1. Time Frame for Reporting

All SAEs and AESIs must be reported to the sponsor or sponsor designee within 24 hours of awareness, regardless of initiation of new anticancer therapy including the following:

- Any SAE or AESI experienced by the subject from the signing of informed consent to 90 days after the last dose of any study drug, regardless of relationship to study drug.
- Any SAE or AESI that the investigator becomes aware of, and believes to be study drug-related, that occurs more than 90 days after the subject last received study drug.

All SAEs must be reported to the following fax line within 24 hours of awareness:

[REDACTED]
[REDACTED]
[REDACTED]

Additional data concerning the SAE (e.g., diagnostic test reports, hospital summaries, etc.) must be promptly reported (within 24 hours of receipt) to the sponsor or sponsor's designee, until resolution of the SAE. Should the FDA or National Regulatory Authorities require that the sponsor submit additional data on the event, the investigator will be asked to provide those data to the sponsor in a timely fashion.

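### Protocol 14.5 makes no exception for serious events, so for pre-dose SAEs judged not protocol-related it contradicts the 24-hour reporting duty in 14.7.1

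*Protocol*

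**What the plan says.** Four parts of the current protocol address events between consent and the first dose of study drug.

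- **14.5 (Determination of Causality).** The investigator judges whether an event before investigational product is protocol-related. Of such events, "only those that are assessed by the investigator as protocol-related should be reported to the sponsor". Seriousness is not mentioned.
- **14.7.1 (Time Frame for Reporting).** The window opens at consent and closes 90 days after the last dose, and every SAE within it is covered "regardless of relationship to study drug". The time limit is mandatory: "All SAEs must be reported to the following fax line within 24 hours of awareness".
- **14.6 (Documenting Adverse Events).** All AEs, with SAEs named explicitly, "are to be accurately recorded on the Adverse Event page of the subject's eCRF from the time the subject signs the informed consent". Section 12.3.1.6 says the same.
- **12.3.2.18, repeating Table 1 footnote h.** "Non-serious events from ICF signature until administration of first study drug that are not study related will be reported as medical history". This exception is confined to events that are not serious.

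Two other sections bear on the point. Section 14.2 also starts the SAE reporting period at ICF signature and has death from disease progression in that period reported as an SAE. Section 14.7.2 repeats the 24-hour duty to notify the sponsor of an SAE.

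**The concern.** A site coordinator with a hospitalised subject in screening has two instructions. The only paragraph written specifically for the pre-dose window says that an event not caused by a protocol procedure need not go to the sponsor. The SAE reporting section says that it must, within 24 hours. Neither refers to the other on this point.

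The stakes are mainly operational. The next study steps are cemiplimab on Day -7 and craniotomy on Day 0, and a serious neurological event in screening bears on eligibility: uncontrolled seizures and clinically significant raised intracranial pressure are exclusion criteria in 9.2. A site that follows 14.5 as written would send no expedited report. There is also a smaller data question. The safety reporting period in 16.4 starts at ICF signature, so SAE displays not limited to treatment-emergent events could differ in completeness from site to site.

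**Working it through.** There is no figure to reproduce. The check is a reading of the rules against each other.

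**Does 14.5 reach serious events?** Yes. Section 14.3.1 makes an SAE a kind of AE: "An AE is considered an SAE if at least one of the following conditions applies". A rule for AEs with no exception therefore includes SAEs.

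**Does 14.7.1 reach pre-dose events?** Yes. Its window opens at consent. Its relationship clause refers to study drug and 14.5 turns on protocol procedures, but 14.7.1 has no relationship condition of any kind, so the difference in wording does not separate the two rules.

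**Case check, events between consent and first dose:**

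- *SAE, protocol-related.* 14.5: report. 14.7.1: report. No conflict.
- *SAE, not protocol-related.* 14.5: not among the events to report. 14.7.1: report within 24 hours. Direct conflict.
- *Non-serious AE, not protocol-related.* 14.5: not reported to the sponsor. Footnote h and 12.3.2.18: medical history. 14.6 and 12.3.1.6: AE page. 14.7.1 does not apply. This is a lesser disagreement about where the event is recorded.

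Section 14.2 supplies an example of the second case. A death from progression after consent but before cemiplimab is to be reported as an SAE, yet it is not due to a protocol procedure, so 14.5 would leave it out.

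**How narrow is the protocol-related category?** Section 14.5 requires that the medical record contain no alternative etiology. In recurrent glioblastoma the tumor will often be one; footnote 5 to Table 2 describes seizures, headache and cerebral edema as common in this population. The conflicting class is therefore not negligible in principle, but no proportion follows.

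**Which outputs could be touched?**

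- *Treatment-emergent tables.* SAP 9.1.1 generally counts events that begin, or worsen, on or after first dose. Pre-dose SAEs mostly stay out.
- *SAE tables and listings.* SAP 9.1.6 mentions both a table of SAEs and treatment-emergent SAE summaries. The titles of Table 14.3.1.11 and Listing 16.2.7.3 do not say treatment-emergent. If these include pre-dose SAEs, they depend on whether sites read 14.5 as also excusing eCRF entry.
- *Screen failures.* SAP 5.1 keeps them out of all listings and analyses, so only subjects later treated can affect the outputs.
- *Overall survival.* It runs from the first dose and is not involved.

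**Exposure.** The scheduled screening window is Day -30 to Day -8, which is 30 − 8 + 1 = 23 days, and SAP 4.4 counts 40 treated subjects. The documents give no screening SAE rate to apply to that exposure.

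**The case against.** The best reply is that the intended rule is easy to find. Section 14.5 is about causality and uses a recommendation; 14.7.1 is the dedicated SAE section and uses a mandate. Sections 14.2 and 14.7.2 support it, and footnote h and 12.3.2.18 confine the pre-dose exception to non-serious events. This stands as evidence of intent: 14.5 most likely lacks a qualifier. It does not remove the contradiction, because 14.5 is the paragraph written for this window and sites should not have to infer which rule on expedited reporting prevails.

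Three stronger readings might be inferred, and the documents do not support them.

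- *Every screening SAE both must and must not be reported.* The two sections agree on protocol-related SAEs. The conflict is confined to those judged not protocol-related.
- *The sponsor and Medical Monitor may never learn of the event.* Sections 14.6 and 12.3.1.6 require SAEs on the eCRF from consent. AE evaluation is scheduled at screening and Day -7 (12.3.2.1 and 12.3.2.2), and Table 1 has eligibility confirmed within 24 hours before cemiplimab. What is likely lost is the 24-hour notice.
- *A definite number of SAEs is affected.* An assumed screening risk of 2% to 10% in 36 to 40 subjects gives 0.02 × 36 = 0.7 to 0.10 × 40 = 4.0, or about 1 to 4 events. Nothing in the documents supports that range. Treating all of these events as inconsistently handled also assumes that every one is not protocol-related and that sites divide between the two sections.

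It would also go too far to say that Table 14.3.1.11 certainly includes pre-dose events. Its title is unrestricted, but SAP 9.1.6 describes the SOC and PT layout for treatment-emergent SAEs. That point is unsettled.

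**Conclusion.** The contradiction is real and limited. For an SAE between consent and first dose that is assessed as not protocol-related, 14.5 as written leaves out a report that 14.7.1 requires within 24 hours. A site following 14.5 would omit that expedited report before cemiplimab and craniotomy.

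The effect on analysis is small: possible inconsistency across sites in any SAE table or listing not limited to treatment-emergent events, with treatment-emergent tables and overall survival essentially unaffected. The number of events cannot be estimated from the documents. The conclusion rests on the current wording and on the definition of an SAE as a type of AE, not on an assumed event rate. It is worth correcting because it concerns expedited safety reporting and the correction costs almost nothing.

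**What to change.** In 14.5, limit the sentence on pre-dose reporting to non-serious events and add a cross-reference stating that all SAEs from consent follow 14.7.1. This uses the qualifier already in Table 1 footnote h and 12.3.2.18.

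As a secondary consistency edit, align 14.6 and 12.3.1.6 with 12.3.2.18, so that all three give the same place of recording for non-serious pre-dose events that are not study related.

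The SAP already counts 40 treated subjects, so a check with sites for unreported pre-dose SAEs before database lock (SAP 4.4.1) would be a sensible companion step.

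The cost is a few sentences of protocol text. The downside is possibly a few extra SAE reports.
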